## **Data analysis for Aim 2.**

Guided by principles of grounded theory, interviews will be analyzed for emergent themes as soon as interviews are transcribed. We will examine study transcripts to identify primary coding categories as well as a range of themes present within each category. Identified coding categories and themes will be organized into a formal code book, and we will extract illustrative quotes. Transcripts then will be formally content coded. If suggested by the data, thematic categories will be refined, merged, or subdivided, and/or new themes created. To ensure coding reliability, summaries will be coded by at least two raters who will discuss discrepancies and reach consensus. Decision trails will be noted and documented.

Quantitative data collected and returned via mail and email by rural primary care providers will be manually converted to an electronic format for data analysis. This data will be used to describe provider-level barriers, such as unawareness of the burden of HIV, HCV and sexually transmitted infections, a related tendency to under-screen for these conditions, and possibly stigmatizing attitudes towards people who inject drugs that may contribute to under-utilization of primary care services by high risk individuals. Insight gained through these surveys may be used for the design of the UH3 phase.

## **Triangulation of data.**

Data from the cross-sectional survey and biological specimen testing (Aim 1) will inform disease prevalence and associated risk behaviors in our initial catchment counties. Data from the quantitative mail and email-based primary care provider survey and qualitative provider and client interviews (Aims 2b/2c) will provide contextual information about drug use, risk behavior, and service access and utilization. These data will be layered onto the compilation of the county-level data and resources (Aim 2a) and a comprehensive summary report will be generated to guide evaluation of which counties are best suited for the implementation phase.

## **Benchmarks for progressing to UH3 phase.**

If the research proposed above is successful, by the end of year 2 we will have established estimates of the burden of infectious diseases in six rural counties, and described service gaps that must be filled in order to ensure that people who inject drugs have access to the complete package of prevention services. We believe that transition to the UH3 phase of the study, which is described below, will be justified if we achieve the following milestones: (1) ***Client reachability:*** We will enroll no fewer than 800 SSP clients who reside in rural communities during the 12-month recruitment period of the UG3 phase. Based on current and historical volume of prevention encounters at Vivent

Health offices, we expect to be able to achieve the recruitment target of 1,200 individuals without difficulty. However, if enrollment is substantially slower than expected, we believe that recruiting at least 2/3 of this number will demonstrate our ability to engage SSP clients in sufficient numbers to answer our research questions and guide implementation of the Client-Based Prevention Home model. (2) **Local service capacity:** We will confirm there are sufficient resources in at least 3 of the 6 targeted counties to ensure it is feasible that SSP clients can utilize all 9 of the essential prevention services. For example, we might not be able to move forward with implementation of the service delivery model if we cannot identify providers who provide MAT or are willing to start provision of this service with support and consultation from the UW Addiction Medicine Program (see “Provider-level interventions” below). (3) **Community stakeholder willingness:** We will confirm that key stakeholders (e.g., MAT providers, County Public Health Officers, Criminal Justice Agencies, others) are supportive of the new prevention services model participating counties. We will obtain letters of support if requested by funders.

### **Data Analysis for Aim 3.**

There is not a single, primary outcome which can be measured to fully evaluate the impact or effectiveness of the intervention. We therefore have proposed a study design that allows us to evaluate the influence of prevention navigation on progress toward a number of health goals. Appendix 2 shows outcomes we propose to measure.

We will use generalized linear mixed models that will allow us to establish linear growth models. Using quarterly assessments, we will analyze growth rates for each outcome and control for time-variant covariates. Additionally the analysis will allow us to assess the effects of interventions outside of our study that may play a role in our outcome.

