## **7.0 STATISTICAL CONSIDERATIONS**

**Sample size and power considerations for Aim 1.** Power to detect a significant impact of the client-centered prevention home model is based on the change in proportion of clients in the 3 target counties who receive the 9 essential services (see Table 1, pg. 2) compared to clients in the 3 non-targeted counties. The design effect for respondent-driven sampling is a complex function of the network structure in the population, and thus, it is difficult to precisely estimate the sample size requirements. Nevertheless, simulation research indicates that the design effect for respondent-driven sampling is likely to be 2 or less, which suggests that a sample twice that of simple random sampling should provide adequate power. We estimate that approximately 10% of all clients will have access to all 9 essential services prior to the study. Applying a design effect of 2, and given a sample size of 800-1200 clients, the study will be powered to detect an increase in service provision of 8-10% (424 subjects per group is sufficient to detect a 10% difference in essential service provision rates; 582 subjects per group is sufficient to detect an 8% difference), assuming 80% power and 5% type I error.

**Sample size and power considerations for Aim 3.** The complexity of our study design requires multiple longitudinal approaches to account for independent and dependent samples. Based on our formative work, an average of 2 clients enrolled per week into the study is feasible for the SSP staff.

With a sample size of 405 (270 intervention and 135 controls), we would have 80% power to detect a difference between 28% and 42% in the same outcome, an effect size that we believe is meaningful and realistic to achieve. In other words, the sample size was chosen to ensure that the Primary Aim 1 comparisons of “Strongly Agree” vs all others of a factor would have sufficient power to detect clinically meaningful increases in accessibility. To address Primary Aim 1, we used preliminary data from the first phase of the study to assume that the base rate of a participant who will strongly agree that it is easy for them to access addiction treatment services is 26%.

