**1.7. Study design.** In order to measure the impact of the Client-Centered Prevention Home we will prospectively assess the 12-week intervention by measuring outcomes at baseline, 3-months, and 6-months. We will target participants who engage in syringe services at Vivent Health and may be interested in additional services that may be offered in our multilevel harm reduction intervention. At intervention sites, the Prevention Navigator will engage prospective clients by screening them for the study, having the participant sign the consent form and performing baseline assessments along with rapid testing for HIV, HCV, and syphilis. Using the same infrastructure used in the UG3 phase, a second group of controls will be enrolled at the three non-intervention sites. Syringe service program staff at the non-intervention sites will recruit participants for baseline, 3-month, and 6-month assessments during the two year study period.

The health-related goals for PWID in the context of this study are multi-faceted, reflecting the heterogeneous needs of this vulnerable population. Accordingly, there is not a single, primary outcome which can be measured to evaluate the impact or effectiveness of the intervention. We therefore have proposed a study design that allows us to evaluate the influence of prevention navigation on progress toward a number of health goals. Because no single study design can account for all of the biases inherent in a non-randomized, multi-county intervention trial, we have proposed 2 different types of comparisons in our evaluation strategy:

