**(B) A comparison of participants enrolled at sites with and without prevention navigation**

In separate analyses, we will compare the self-reported outcomes of individuals enrolled at Vivent Health offices offering only standard prevention services without prevention navigation. This is advantageous for detecting changes over 6 months of follow-up.

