**Steps to reduce discomfort or anxiety resulting from study participation.** Assessment measures involve sensitive topics related to safety and wellness. Some participants may feel awkward or embarrassed when discussing, hearing about, or being asked to provide information related to their safety and wellness. Staff are trained to employ techniques that prevent, reduce, or minimize embarrassment, discomfort, or atypical stress associated with study participation. Staff will be trained to observe for any evidence that a participant may be overly anxious and to assess whether threat sensitization and vulnerability perceptions are realistic. Vivent Health and research field staff will be required to have extensive research- or program-based experience with the conduct of HIV-related research. The project will be guided by a detailed procedural manual, and field staff will receive intensive training focused on the specific project protocols and materials to ensure that they are being rigorously and consistently implemented, including extensive role-play rehearsal of recruitment, enrollment, and consent procedures and assessment procedures and materials. The field team will meet regularly to discuss implementation issues and areas warranting additional training. If research personnel change during the course of the study, new staff will be required to complete the training described above prior to conducting any research activities.

**HIV and HCV testing and counseling safeguards.** All testing staff have completed the Wisconsin AIDS/HIV Program state HIV test counselor training to ensure that HIV pre- and post-test counseling is conducted in accordance with state guidelines. Vivent Health is a CLIA-certified HIV test site funded, in part, by the Wisconsin Division of AIDS/HIV's HIV testing program.

Specimens will only be sent for confirmatory testing for those rapid tests that they are already positive for, therefore, no new health information will be generated by analysis of these samples.

In the UH3 phase of the study, participants who receive the Client-Centered Prevention Home intervention are expected to achieve more positive health outcomes and better linkages to services and care than people who do not receive this intervention.

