In the past 3 months, have you gotten buprenorphine shots – like Sublocade – from a doctor or program?	Intermediate Client-level	ACASI Survey	Change in frequency	✓ T 0 , T 1 , T 2

If I wanted to start medical treatment for opioid or heroin addiction, I could easily get buprenorphine or Suboxone or Subutex.	Short-term Client-level	ACASI survey	Change in Likert-scale	T 0 , T 1 , T 2
If I wanted to start a medical treatment for opioid or heroin addiction, I could easily get into a methadone program	Short-term Client-level	ACASI survey	Change in Likert-scale	T 0 , T 1 , T 2
Any outpatient visit for MAT for opioid use disorder post initiation of CCPH or control	Intermediate Client-level	Medicaid	Change in frequency	✓ T -2 , T 0 , T 2
Prescription fill for methadone, buprenorphine, naltrexone, probuphine post initiation of CCPH or control	Long-term community-level	Medicaid	Change in frequency	✓ T -2 , T 0 , T 2
Treatment for hepatitis C				
Utilization of HCV treatment among participants	Intermediate Client-level	Medicaid	Change in rate of HCV treatment	✓ T 0 , T 1 , T 2
Successful HCV treatment among participants	Long-term Client-level	WEDSS	Change in cure rate of HCV treatment	T -4 , T 0 , T 4
Decrease in prevalence of HCV	Long-term County-level	WEDSS	Change in rate of HCV by county	T -4 , T 0 , T 4
Do you currently have health insurance or health care coverage?	Short-term Client-level	ACASI Survey	Change in rate of health insurance	T 0 , T 1 , T 2
If I ever tested positive for hepatitis C, I'm confident I could get linked to a medical expert and start hepatitis C treatment.	Short-term Client-level	ACASI Survey	Change in Likert-scale	T 0 , T 1 , T 2
Number of appointments made for HCV treatment	Short-term Client Level	CCPH Program data	Change in frequency	T 0 , T 1 , T 2
Prescription fill for DAAs post initiation of CCPH or control	Intermediate Client-level	Medicaid	Change in frequency	✓ T -2 , T 0 , T 2
Lower risk of viral hepatitis				

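### Aim 3 tests dozens of Appendix 2 outcomes with no primary contrast, hierarchy or error control, so a falsely favourable result is about 25% to 37% likely rather than 2.5%

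*Combined protocol and SAP*

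**What the plan says.** Section 6.0, Data Analysis for Aim 3, opens with "There is not a single, primary outcome which can be measured to fully evaluate the impact or effectiveness of the intervention". The same position appears in section 5.4 (Prevention Navigation) and in Appendix 1, section 1.7. Section 6.0 continues: "Appendix 2 shows outcomes we propose to measure". It then says of the mixed models: "we will analyze growth rates for each outcome and control for time-variant covariates".

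Appendix 1, section 1.7 announces "we have proposed 2 different types of comparisons in our evaluation strategy" and then lists three:
- **A:** within-person, pre/post, at the intervention sites.
- **B:** intervention versus non-intervention sites, introduced with "In separate analyses, we will compare the self-reported outcomes of individuals enrolled at Vivent Health offices".
- **C:** a cohort comparison of longer-term outcomes from external data.

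Two other places point to a deciding outcome, and they differ:
- Section 2.0 (Aim 3) and Appendix 1, section 1.3 name the proportion of clients receiving the package of essential services (nine services in section 2.0). That composite is not a row of Appendix 2.
- Section 7.0 sizes Aim 3 at 270 intervention and 135 control participants for 80% power to detect 28% versus 42%. It says that comparisons of Strongly Agree against all other answers "would have sufficient power to detect clinically meaningful increases in accessibility". The contrast is labelled Primary Aim 1 and concerns ease of access to addiction treatment. It is tied to no Appendix 2 row, time point or comparison.

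No alpha, hierarchy, multiplicity adjustment or exploratory label is given for Aim 3. Section 6.0 calls only Aim 1 descriptive.

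**The concern.** Aim 3 is framed as an evaluation of impact and carries a confirmatory-style power statement. Yet nothing fixes in advance which result would show that navigation works. Each survey item can produce a result in A and another in B. The two can disagree, and the plan does not say which prevails.

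At stake is the error rate of the conclusion. The 5% behind the power figure belongs to one test. It does not belong to a conclusion drawn from whichever of several dozen results turn out nominally significant. Someone who wants to know afterwards whether the trial succeeded would have three candidate answers in the document (the service package, the access contrast, any Appendix 2 row) and no rule for choosing among them.

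**Working it through.** **1. Reproduce the stated power.** Inputs from section 7.0: n = 135 and 270, p = 0.28 and 0.42, difference 0.14. Alpha is not stated for Aim 3. I take 0.05 two-sided, because the Aim 1 paragraph uses 5% and the COVID-19 pilot paragraph is two-sided.

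- Pooled p = (135×0.28 + 270×0.42)/405 = 0.3733
- SE under no difference = √[0.3733×0.6267×(1/135 + 1/270)] = 0.0510
- SE under the alternative = √[0.28×0.72/135 + 0.42×0.58/270] = 0.0489
- Power, pooled = Φ[(0.14 − 1.96×0.0510)/0.0489] = Φ(0.82) = 79.4%
- Power, unpooled = Φ(0.14/0.0489 − 1.96) = Φ(0.90) = 81.6%

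The stated 80% is therefore the power of a single unadjusted two-sided 5% test. A one-sided test would give 87.4%. At 0.05/28 (critical value 3.12) the same formulas give 34.7% and 39.6%.

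**2. Count the outcomes.** Appendix 2 rows by domain: addiction treatment 13, hepatitis C treatment 7, viral hepatitis risk 5, HIV risk 10, overdose 5, smoking 4, self-stigma 5; total 49. The item "I could easily get into a methadone program" appears twice, so 48 are distinct. ACASI rows number 29, or 28 distinct.

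**3. Chance of at least one nominally significant result if the program has no effect.** For k tests with common correlation ρ:

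- Favourable direction (0.025 per test): 1 − ∫ Φ[(1.96 − √ρ·u)/√(1−ρ)]^k φ(u) du. At ρ = 0 this is 1 − 0.975^k; for k = 28, 50.8%.
- Either direction: the same, with Φ[(−1.96 − √ρ·u)/√(1−ρ)] subtracted inside the power. At ρ = 0 this is 1 − 0.95^k; for k = 28, 76.2%.
- A or B together: simulated. Both statistics for an item use the intervention arm's changes. With equal variances their correlation is √[(1/270)/(1/270 + 1/135)] = √(1/3) = 0.58.

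| Family | Favourable, ρ = 0.5 (ρ = 0 to 0.8) | Either direction, ρ = 0.5 (ρ = 0 to 0.8) |
|---|---|---|
| One test | 2.5% | 5% |
| 28 items, B only | 25% (51% to 12%) | 49% (76% to 25%) |
| 28 items, A or B | 37% (71% to 20%) | 70% (92% to 40%) |
| 48 rows, once each | 31% (70% to 15%) | 61% (92% to 30%) |

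The A-or-B figures are accurate to about one percentage point. The correlations are assumptions, since the documents give none.

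**The case against.** **Many outcomes are legitimate here.** The clients' needs differ, and the plan says so openly. That justifies measuring many things. It does not justify leaving the deciding result open.

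**The sizing contrast in section 7.0 could serve as a de facto primary.** It comes closest, and it does state a difference regarded as meaningful. But sections 5.4 and 6.0 and Appendix 1 disclaim any primary outcome, section 2.0 names a different endpoint, and the contrast matches no single Appendix 2 row. Appendix 2 has separate methadone and buprenorphine access items, scored as change in Likert scale.

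**A reader might infer that an ineffective program would more likely than not appear effective.** The documents do not support that. Only results in the program's favour could be reported as effectiveness, and those stay below 50% for A or B once ρ passes about 0.3. The figures above one half mostly count either direction at low or moderate correlation.

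**A reader might also infer that each outcome is tested three times.** It is not. Self-reported items belong to A and B, external data to C. The text on A is ambiguous too: it calls A suited to short-term outcomes, and only 8 distinct ACASI items carry that label. With A on 8 items and B on 28, the figures at ρ = 0.5 are about 30% favourable and 59% in either direction.

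**The 48-row line is only indicative.** Eleven rows are county-level, and no test on the 405 participants is described for them. I do not rest the conclusion on it.

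**No significance threshold is stated for Aim 3.** True; 0.05 is assumed. The statement in Appendix 1, section 3.1 that recipients "are expected to achieve more positive health outcomes and better linkages to services and care than people who do not receive this intervention" is benefit language and not an analysis rule.

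**Conclusion.** The point stands. The plan evaluates effectiveness on a large family of outcomes, declines to name a primary, and sets neither error control nor a rule for which result governs, while its sample size assumes one unadjusted test. For the 28 survey items the chance of a falsely favourable nominal result is about ten times the single-test 2.5% in B alone (25%). It is about fifteen times in A or B (37%). Even at ρ = 0.8 it is 12% and 20%.

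This rests on 0.05 two-sided per test, exchangeable correlation, and all 28 items being run through A for the larger figure. It also takes every test to be valid at its nominal level. Bias from an uncontrolled pre/post comparison and from non-randomized sites is not included.

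**What to change.** Reconcile section 2.0 and Appendix 1 section 1.3, the no-primary statements (sections 5.4 and 6.0, Appendix 1 section 1.7), and section 7.0, as follows.

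1. **Primary.** Name one contrast in comparison B. The default is the Strongly Agree access contrast of section 7.0, tied to a named Appendix 2 item (methadone access, buprenorphine access, or a defined combination), at one stated time point, two-sided 0.05. Estimate it as a baseline-adjusted group difference in change, through the group-by-time term of the planned mixed model. A raw follow-up proportion would let pre-existing differences between non-randomized sites decide the result. In choosing the time, note that Appendix 1 values B for change over 6 months, whereas section 5.4 gives intervention participants enrolled in February and March 2023 no 6-month survey.
2. **Service package.** State the role of the 9-service endpoint: primary, secondary or descriptive.
3. **Secondaries.** One lead outcome from each of the other six domains, in B, Holm-adjusted, tested only if the primary succeeds.
4. **Everything else.** Label the remaining rows, comparison A and comparison C supportive or exploratory, reported as estimates with 95% confidence intervals.

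The cost is protocol and SAP wording, with no new data or participants. The downside is that most Appendix 2 rows can no longer support a stand-alone effectiveness claim. A single primary avoids the multiplicity penalty; Bonferroni over 28 items would leave about 35% to 40% power. It does not by itself secure 5% error or 80% power, because allocation is by three sites against three. Power should be restated for the contrast finally named.

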In addition to confirming there are sufficient resources in the study areas, our research showed that the 3 selected communities differ from each other in notable ways, which will provide opportunities to study how implementation strategies may differ in varying contexts. For example, Brown County was unique in that the RDS survey engaged a much higher than expected number of Native American respondents. Respondents in Brown County also more commonly listed heroin as their “drug of choice,” while respondents in all other sites indicated methamphetamine was their preferred drug.

**COVID-19 Response and Amended Intervention.** In response to the national crisis, and to best serve PWID in rural WI, we will recruit subjects in our 3 intervention sites (Brown, Marathon, and La Crosse Counties). Additionally, we will be resampling participants who were enrolled in the UG3 phase of the study and who have given permission to be contacted about future research opportunities. Each navigator will have a case load of no more than 15 participants at one time throughout the course of this pilot. Once we have concluded the pilot in Sept 2020, we will resume aim 3 procedures.

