### **Participant recruitment for Aim 3 (UH3 Phase, 2019-2021).**

Based on preliminary data, burden of opioid-related illness, and familiarity with supportive local stakeholders, we selected La Crosse County, Marathon County, and Brown County as the implementation sites for this study. Eau Claire, Douglas, and Outagamie Counties will serve as the

nonintervention sites, where participants will receive services as usual. In the fall of 2019, 3 full-time Prevention Navigators were hired and trained to conduct the intervention. Participants in this phase of the study will be recruited into one of two groups, Prevention Navigation, or usual services. Beginning in year 3, SSP clients at the 6 selected Vivent Health sites will be notified about the study by prevention specialists or SSP staff if the client 1) tests for HCV or HIV at the SSP, 2) inquires about services that may be in the prevention home through casual conversation, 3) the client engages in naloxone training, 4) through posted materials of the availability of new resources for improving prevention services and linkages to treatment in the SSP and community offices, 5) recruit through flyers and posted materials in the SSP and local community resource offices, and public areas, 6) through Vivent Health Facebook advertisements, 7) through our study website listed on our flyers, and/or 8) through respondent-driven sampling (RDS). Upon the completion of the first two attended Prevention Navigation sessions,

participants will be given a referral coupon and asked to refer one eligible peers per coupon to participate in the study. Vivent Health will dispense coupons that have been prepared by UW research staff. SSP clients at the nonintervention sites will be recruited at the time the Vivent Health staff member assists them with regular exchange services. Nonintervention sites will aim to enroll about one participant every-other week.

[figure not shown]
[figure not shown]

Figure 5. Parallel crossover (wait-list control) and cross-site study design

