The goal of the Client-Centered Prevention Home program is to increase the knowledge of people who inject drugs on navigating prevention and treatment services for HIV, HCV, and drug overdose. We describe measures for our study population in the Appendix. Key sources for measurement will come from the ACASI survey that will be adapted from the ROI Harmonized UG3 survey, surveillance data gathered from the state of Wisconsin, and Medicaid health utilization data.

**1.4. Study data collection sites.** The main community partner, Vivent Health, will serve as the data collection and study site. Vivent Health is a statewide organization that provides harm reduction services, including syringe services and confidential HIV and HCV testing. As shown in Figure 1, three sites will be used for the intervention of the study: Brown County (Green Bay), Marathon County (Wausau), and La Crosse County (City of La Crosse). The 3 other Vivent Health offices that participated in the UG3 study phase, including Outagamie County (Appleton), Eau Claire County (City of Eau Claire), and Douglas County (Superior), will serve as recruitment sites for control group participants during the UH3 phase, but will not provide the prevention navigation intervention.

**1.5. Study sample description and inclusion and exclusion criteria.** Leveraging relationships developed among Vivent Health clients and community partners during the UG3 phase, we will recruit participants using Vivent Health staff at all six counties. In order to be part of the study, participants must meet the following eligibility criteria: 1) clients must be at least 18 years old, 2) have injected drugs to get high in the past 30 days, and 3) reside in one of the participating communities in or around one of the six participating counties.

Exclusion criteria are: (1) not speaking English fluently, (2) residing outside or being unwilling or unable to travel for study visits at one of the participating communities.

**1.6. Sample size.** A total of 405 participants will be enrolled to evaluate the intervention (Figure 1). Study procedures will vary for participants based on enrollment into 2 study groups, as follows:

- (a) 270 participants enrolled at intervention sites, who will receive prevention navigation.
- (b) 135 participants enrolled across the 3 non-intervention sites, who will serve as a contemporaneous control group.

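### Aim 3 assigns navigation by office (3 vs 3) but names no office term; if only participant-level effects are fitted, comparison (B) has intervals that are too narrow wherever change varies by office

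*Combined protocol and SAP*

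**What the plan says.** **Who gets the intervention.** Arm follows office and is not randomized. Appendix 1, section 1.4 states that "three sites will be used for the intervention of the study: Brown County (Green Bay), Marathon County (Wausau), and La Crosse County". The Outagamie, Eau Claire and Douglas offices recruit the controls. Section 4.0 (recruitment for Aim 3) adds that "3 full-time Prevention Navigators were hired and trained to conduct the intervention". Appendix 1, section 1.6 plans 270 participants at the intervention offices and 135 at the others.

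**The model.** Section 6.0, Data Analysis for Aim 3, says "We will use generalized linear mixed models that will allow us to establish linear growth models", with growth rates estimated for each outcome and adjustment for time-varying covariates. It names no random effect at any level, no office or county term, no cluster-robust error and no small-sample method.

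**The comparison.** Under comparison (B) in Appendix 1, section 1.7, "we will compare the self-reported outcomes of individuals enrolled at Vivent Health offices offering only standard prevention services without prevention navigation". No model or standard error is given there.

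**The power statement.** Section 7.0 says "With a sample size of 405 (270 intervention and 135 controls), we would have 80% power to detect a difference between 28% and 42" (per cent). Neither alpha nor sidedness is stated for Aim 3; the nearest text, "assuming 80% power and 5% type I error", belongs to the Aim 1 paragraph. The only design effect in the documents is for respondent-driven sampling, also under Aim 1.

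**The concern.** Navigation is delivered to whole offices, so the arm contrast in comparison (B) carries the variation between six offices as well as the variation between 405 people. If offices differ in how their clients change over time, people at the same office share part of that change. A model with participant effects only would count it as many independent observations. Its standard error would then be too small, and a nominal 5% test would reject too often.

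Such variation is plausible. Local service changes affect one county at a time, and only three navigators deliver the intervention. Comparison (B) is the only contemporaneous controlled comparison of the survey outcomes, and Appendix 2 lists many of them. Leaving the office level open also lets the choice be made after the data are seen.

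**Working it through.** **Inputs from the documents.** 270 and 135 participants; 28% and 42%; three offices per arm.

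**Assumptions.** Two-sided alpha 0.05; even enrolment, so 90 and 45 per office; complete follow-up; office ICC *r* from 0 to 0.05, because the documents give none.

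**Step 1: reproduce the stated power with independent participants.**
- Pooled proportion: (135 × 0.28 + 270 × 0.42)/405 = 0.3733.
- Null SE: √[0.3733 × 0.6267 × (1/135 + 1/270)] = 0.0510.
- Alternative SE: √[0.28 × 0.72/135 + 0.42 × 0.58/270] = 0.0489.
- Power: Φ[(0.14 − 1.96 × 0.0510)/0.0489] = Φ(0.82) = 79.4%.

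An arcsine calculation gives 79.9%. The 80% therefore contains no allowance for office. (Section 7.0 also gives the base rate for "easy for them to access addiction treatment services is 26" per cent, while the power sentence uses 28%. That is a separate inconsistency.)

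**Step 2: variance inflation if office is left out.**
*f* = [(1 + 89*r*)/270 + (1 + 44*r*)/135] / [1/270 + 1/135] = 1 + 59*r*.
The true SE is √*f* times the participant-level SE. In a growth model, stable baseline differences between offices cancel from the arm-by-time term, so *r* here is the ICC of the change.

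**Step 3: actual type I error of the nominal 5% test.**
2 × [1 − Φ(1.96/√*f*)]. For *r* = 0.01: *f* = 1.59, √*f* = 1.261, 1.96/1.261 = 1.554, giving 12.0%.

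**Step 4: power for 28% vs 42% with office accounted for.**
Noncentral t on 6 − 2 = 4 df, noncentrality 0.14/(0.0489√*f*), critical value 2.78. At *r* = 0 the noncentrality is 2.86 and power is 58%. In this step *r* is the ICC of the outcome compared between arms.

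| Assumed ICC | *f* | SE ratio | Type I error | Simulated | Power, 4 df |
|---|---|---|---|---|---|
| 0 | 1.00 | 1.00 | 5.0% | 4.9% | 58% |
| 0.001 | 1.06 | 1.03 | 5.7% | not run | 56% |
| 0.005 | 1.30 | 1.14 | 8.5% | 8.0% | 48% |
| 0.01 | 1.59 | 1.26 | 12.0% | 11.7% | 41% |
| 0.02 | 2.18 | 1.48 | 18.4% | 19.3% | 32% |
| 0.05 | 3.95 | 1.99 | 32.4% | 32.7% | 20% |

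The simulated column is a person-level t-test on simulated 6-month changes, 4,000 runs per ICC. In the same runs, a t-test on the six office means rejected in 4.7% to 5.4%.

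**Step 5: sensitivity to dropout.** With 20% loss as an illustration (72 and 36 per office), *f* = 1 + 47*r*. At *r* = 0.01, *f* = 1.47 and type I error is 10.6% instead of 12.0%.

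**The case against.** **Silence is not exclusion.** A reader might infer that the plan commits to a model ignoring office. It does not. Section 6.0 lists no random effects at all, and a generalized linear mixed model can carry an office level. This stands, so the error rates apply only if participant-level effects alone are fitted.

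**The size is assumed.** A reader might also infer that the false-positive rate is well above 5% for every survey outcome. The documents give no ICC. At 0.001 the rate is only 5.7%; it reaches 12% or more from about 0.01 upward. Appendix 2 mixes access items, service use, sexual risk, smoking and stigma, and nothing shows that change in each varies by office. Sections 9.0 (D) and 5.4 expect some missing or omitted assessments, which lowers the inflation somewhat at a given ICC. All of this stands.

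**The evidence on communities is indirect.** Section 3.0 says "our research showed that the 3 selected communities differ from each other in notable ways", but it describes baseline composition among the intervention communities only. Stable differences of that kind cancel from arm-by-time. Section 4.0 reports three navigators without expressly placing one per office. So office variance in change is plausible, not shown.

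**The plan acknowledges bias.** Appendix 1, section 1.7 concedes that the design is non-randomized and adds the within-person comparison (A). Section 6.0 also intends to adjust for time-varying covariates and to consider outside interventions. These bear on bias from local events. They do not supply a standard error that reflects six offices.

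**Conclusion.** The point holds in conditional form. Arm is set by six offices, the analysis text leaves the office level unspecified, and the 80% power figure holds only with independent participants. If only participant-level effects are fitted, any office variance in change makes the intervals for comparison (B) too narrow. Type I error is then about 6% to 32% for assumed ICCs of change from 0.001 to 0.05, with even enrolment and complete follow-up.

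The documents do not support a statement that the rate is certainly high, or that it is inflated for every outcome. Comparison (A) is not a between-office contrast and is outside this point. The matter is worth settling now because the remedy is analysis wording, and because comparison (B) has less power than Section 7.0 states.

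**What to change.** **Section 6.0, Data Analysis for Aim 3.** State that, for comparison (B), the arm-by-time contrast is tested at office level with about 4 degrees of freedom, by one method fixed in advance that suits binary and Likert outcomes. One example is a t-test on the six office mean changes (change in proportion or in mean score), with any covariate adjustment done first at person level. State which change enters the office mean, since some late intervention enrollees have no 6-month survey. Show the six office-level changes beside each estimate.

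A random office slope with Kenward-Roger degrees of freedom is less suitable as the single rule. That correction was built for linear mixed models and does not carry over directly to the binary 'Strongly Agree' outcome. Changing tests when the office variance is estimated as zero would make the choice depend on the data.

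**Section 7.0.** State that the 80% assumes independent participants, and that power for 28% vs 42% with office accounted for is about 58% at ICC 0, 41% at 0.01 and 32% at 0.02.

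**Cost.** No new data or sites are needed. The price is precision: the critical value rises from 1.96 to 2.78, so intervals are 2.78/1.96 = 1.42 times as wide even at ICC 0, and 1.42 × 1.26 = 1.79 times at ICC 0.01. The change corrects the standard error only. Confounding from the non-random choice of offices remains and should be stated as a limitation.
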